In Part A, NM21-1480 (dose levels 1 through 7 in the escalation phase) will be administered as a single IV infusion every 14 days for a total of 2 infusions per treatment cycle (4 weeks). Each treatment cycle comprises 2 doses of study drug administered on Days 1 and 15. Treatment for the second cycle is administered on Days 29 and 43, with a response assessment between Days 52 and 56 after the first dose of every other treatment cycle in Part A (i.e., every 8 weeks at the “8-Week Assessment”, see [Table 7-1](#) for details). In Part A, response assessment between Days 52 and 56 and between Days 108 and 112, respectively, is conducted for all patients still in the study, independent of the number of study drug administrations received during the previous 8-week/2-treatment cycles. Following each treatment cycle, the decision to treat a patient with additional cycles of NM21-1480 will be based on tolerability of the study drug and tumor response evaluation performed every 8 weeks i.e., in the week prior to administration of NM21-1480 in all odd number treatment cycles (e.g., Cycles 3, 5, 7, etc.). For optional Part A-2 and Part B, depending on SMC decision on dose levels and dosing intervals to be chosen for this expansion cohort phase, treatment cycles and dosing intervals may remain the same as described above for Part A (i.e., dosing intervals of approximately 14 days). In Part B of the study, NM21-1480 will thus be administered as a single IV infusion approximately every 14 days at the 800mg flat dose, based on Part A PK data which do not indicate substantial accumulation over time with this dosing interval; the 800mg dose of NM21-1480 thus represents presumptive RP2D to be further studied in Part B. Optional Part A-2 of the study will explore one more higher dose level (1400mg flat dose with approximately 14-day dosing interval) than was studied in Part A. Such 1400mg dose level will be explored applying strict stopping criteria and respecting a 28-day DLT evaluation period before more than 6 subjects are exposed. PK data for this 1400mg dose level in Part A-2 will be closely followed and in case of observation of relevant drug accumulation over time, the dosing interval for this dose may be adjusted to approximately every 21 days, resulting in treatment cycles of 6 weeks in such case. In optional Part A-2 and Part B of the study, response assessment is done every 6 weeks for the first 24 weeks patients are on active treatment, before switching to a response assessment every 8 weeks thereafter. Following each response assessment in optional Part A-2 and Part B, the decision to treat a patient with additional dose administrations of NM21-1480 will be based on tolerability of the study drug, perceived clinical benefit and tumor response evaluation performed every 6 weeks (first 24 weeks) or 8

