7.1.6 Schedule of Assessments

Table 7-1 Schedule of Assessments (2-week Dosing Interval; APPLIES TO ALL PARTS [A, A-2 AND B] OF THE STUDY)

Period	Screening Period*		Treatment Period ^d (2-week Dosing Interval/4-Week Treatment Cycles)				Follow-up Period ^a	Survival Follow-up ^b
Visit Name	Pre-Screen (Cohorts B2, B3, B5 and B8 only) ^{bb,dd,ee}	Screening	Cycle Day 1 Treatment Visit ^e	Cycle Day 15 Treatment Visit ^e	Cycle 1 Day 21±3 ^{gg} (Biopsy Visit)	Imaging and Treatment Response Assessment Visits ^c	Follow-up (FU) 1, FU2, and FU3 Visits	
Time point (Day / Week)	Day -42 to -29	Day -28 to -1	C1: Day 1 / Week 1 C2: Day 29±2 / Week 5 C3: Day 57±3 / Week 9 C4: Day 85±3 / Week 13 C5: Day 113±3 / Week 17 C6: Day 141±3 / Week 21 C7: Day 169±3 / Week 25 C8: Day 197±3 / Week 29	C1: Day 15±2 / Week 3 C2: Day 43±2 / Week 7 C3: Day 71±3 / Week 11 C4: Day 99±3 / Week 15 C5: Day 127±3 / Week 19 C6: Day 155±3 / Week 23 C7: Day 183±3 / Week 27 C8: Day 211±3 / Week 31 ^e		Day 39-43 / Week 6 (Pt A-2 and B only) Day 52-56 / Week 8 (Pt A only) Day 79-85 / Week 12 (Pt A-2 and B only) Day 108-112 / Week 16 (Pt A only) Day 120-127 / Week 18 (Pt A-2 and B only) Day 164-168 / Week 24 (Pts A, A-2 and B) Day 220-224 / Week 32 (Pts A, A-2 and B) ^c	FU1: 0 to 30 days post discontinuation FU2: 60 days ± 7 post discontinuation FU3: 90 days ± 7 post discontinuation	Every 3 months ± 7 days
ICF/HIPAA ^f	x ^{bb}	x						
Eligibility Criteria		x						
Demographics & medical history ^{g,h}		x						
Diagnosis & confirmation stage		x						
Tumor-specific therapy history ^{ff}		x						
Hepatitis B and C, & HIV testing ⁱ		x						
CD4 T-cell count ^l		x						
Covid-19 vaccination confirmation or negative Covid-19 polymerase chain reaction (PCR) test		x						
NM21-1480 infusion ^g			x	x				
Vital signs ^k		x	x	x			x	
Height		x						
Weight		x	x (Odd-numbered cycles only)				x (FU1 only)	
Physical exam ^l		x	x	x			x	
Oxygen saturation ^m			x	x				
ECOG performance		x	x	x			x	

Period	Screening Period*		Treatment Period ^d (2-week Dosing Interval/4-Week Treatment Cycles)				Follow-up Period ^a	Survival Follow-up ^b
Visit Name	Pre-Screen (Cohorts B2, B3, B5 and B8 only) ^{bb,dd,ee}	Screening	Cycle Day 1 Treatment Visit ^c	Cycle Day 15 Treatment Visit ^c	Cycle 1 Day 21±3 ^{gg} (Biopsy Visit)	Imaging and Treatment Response Assessment Visits ^c	Follow-up (FU) 1, FU2, and FU3 Visits	

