 - ff. Mandatory fresh, paired biopsy to be taken during screening period and at Day 28±3. **This only applies to patients with mCRC enrolled to Cohort B8.** The on-treatment biopsy can be delayed to the next clinically feasible day closest to Day 28 in situations in which as per investigator judgement taking the biopsy is not clinically feasible at the scheduled day. In any case, on-treatment biopsies should not be taken at days of dosing with NM21-1480. Both baseline as well as matched on-treatment biopsies. Fresh biopsies can be taken from primary tumor or metastases. At least 3 biopsy cores, but preferably more if considered safe by the radiologist, shall be taken at each biopsy event and touch preparation as per site standard approach shall be applied to ensure specimen adequacy (i.e., confirm tumor content). Further details are described in the laboratory manual. In addition to these fresh biopsies, for patients for whom there is archival primary tumor tissue available, this archival tissue, as per inclusion criterion 3 requirements shall also be provided for biomarker analysis.
 - gg. Only applicable for mCRC patients enrolled to Cohort B8.
 - hh. Not applicable to patients in Cohort B5 randomized to standard-of-care anti-PD1 therapy only.

7.1.7 Blood Sampling Schedule (APPLIES TO ALL PARTS [A, A-2 AND B] OF THE STUDY)

Table 7-3 Pharmacokinetics, Anti-Drug Antibody, and Pharmacodynamic Blood Sampling Schedule (2-week Dosing Interval)

		PK ^{a,b, j}	ADA ^j	IPT	sPD-L1/ sCD137	Cytokines	RO	ctDNA ^k	PD-L1 IHC	TMB, TCRseq, & MSI by DNA Analysis	mRNA/ IF	DNA, mRNA, IHC ^h
Visit name / Study day	Time Point	Serum	Serum	Whole Blood	Serum	Serum	Whole Blood	Whole Blood	Biopsy (FFPE)	Biopsy (FFPE)	Biopsy (FFPE) ^c	Mandato ry Biopsy ^h
Screening / Day -28 to -1	--							x ^k	x	x	x	x
Cycle 1, Day 1 / Study Day 1	Pre-dose	x ^g	x ^g	x ^g	x ^g	x ^g	x ^g	x ^k				
	EOI ^f ± 5 min	x ^g			x ^g	x ^g	x ^g					
	4 h ± 10 min	x ^d										
	8 h ± 1 h	x ^d										
Cycle 1, Day 2 / Study Day 2	24 h ± 2 h	x ^d			x ^d	x ^d	x ^d					
Cycle 1, Day 3 / Study Day 3	48 h ± 4 h	x ^d										
Cycle 1, Day 5 / Study Day 5	96 h ± 12 h	x ^d			x ^d		x ^d					
Cycle 1, Day 8 / Study Day 8	168 h ± 24 h	x ^g	x ^g	x ^g	x ^g	x ^g	x ^g					
Cycle 1, Day 15 / Study Day 15 ± 2	Pre-dose	x ^g	x ^g	x ^g	x ^g	x ^g	x ^g	x ^k				
Cycle 1, Day 21 / Study Day 21 ± 3	--											x ^l

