		PK ^{a,b, j}	ADA ^j	IPT	sPD-L1/ sCD137	Cytokines	RO	ctDNA ^k	PD-L1 IHC	TMB, TCRseq, & MSI by DNA Analysis	mRNA/ IF	DNA, mRNA, IHC ^h
Visit name / Study day	Time Point	Serum	Serum	Whole Blood	Serum	Serum	Whole Blood	Whole Blood	Biopsy (FFPE)	Biopsy (FFPE)	Biopsy (FFPE) ^c	Mandato ry Biopsy ^h
Cycle 2, Day 1 / Study Day 29 ± 2	Pre-dose	x ^g	x ^g	x ^g	x ^g	x ^g	x ^g	x ^k			x	
Cycle 2, Day 8 / Study Day 36 ± 2	168 h ± 48 h	x ^g	x ^g	x ^g	x ^g	x ^g	x ^g					
Cycle 2, Day 15 / Study Day 43 ± 2	Pre-dose	x ^g	x ^g		x ^g	x ^g		x ^k				
Cycle 3, Day 1 / Study Day 57 ± 3	Pre-dose	x ^g	x ^g	x ^g	x ^g	x ^g	x ^g	x ^k			x	
	EOI ^f ± 5 min	x ^g										
	4 h ± 10 min	x ^d										
	8 h ± 1 h	x ^d										
Cycle 3, Day 2 / Study Day 58	24 h ± 2 h	x ^d				x ^d						
Cycle 3, Day 3 / Study Day 59	48 h ± 4 h	x ^d										
Cycle 3, Day 5 / Study Day 61	96 h ± 12 h	x ^d										
Cycle 3, Day 8 / Study Day 64	168 h ± 24 h	x ^g				x ^g						
Cycle 3, Day 15 / Study Day 71 ± 3	336 h ± 48 h	x ^d						x ^k				

		PK ^{a,b, j}	ADA ^j	IPT	sPD-L1/ sCD137	Cytokines	RO	ctDNA ^k	PD-L1 IHC	TMB, TCRseq, & MSI by DNA Analysis	mRNA/ IF	DNA, mRNA, IHC ^h
Visit name / Study day	Time Point	Serum	Serum	Whole Blood	Serum	Serum	Whole Blood	Whole Blood	Biopsy (FFPE)	Biopsy (FFPE)	Biopsy (FFPE) ^c	Mandato ry Biopsy ^h
All subsequent even-numbered cycles, Days 1 and 15 / Study Days e.g., 85 ± 3, 99 ± 3, 141 ± 3, 155 ± 3, etc.								x ^k				
All subsequent even-numbered cycles, Day 8 / Study Days e.g., 92 ± 3, 148 ± 3, 204 ± 3, etc.	168 h ± 48 h	x ^g	x ^g	x ^g	x ^g	x ^g	x ^g					
All subsequent odd-numbered cycles, Day 1 / Study Days 113 ± 3, 169 ± 3, etc.	Pre-dose	x ^g	x ^g	x ^d	x ^d	x ^d	x ^d	x ^k		x		
All subsequent odd-numbered cycles, Day 15 / Study Days e.g., 127 ± 3, 183 ± 3, etc.								x ^k				
Follow-up Period	--	x (FU1 only)	x (FU1 only)					x ^k (FU1, FU2, and FU3)				

Abbreviations: ADA = Anti-drug antibodies; D = Dose (study drug administration); DNA = Deoxyribonucleic acid; EOI = End of infusion; FFPE = Formalin-fixed paraffin-embedded; h = Hour; IHC = Immunohistochemistry; IPT = Immunophenotyping; TMB = Tumor mutational burden; MSI = Microsatellite instability; IF = Immunofluorescence;

PK = Pharmacokinetics; PD-L1 = Programmed death-ligand 1; mRNA = Messenger Ribonucleic acid; RO = Receptor occupancy; TCRseq = T-cell receptor sequencing; TMB = Tumor mutational burden

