*Assessment of IPT, sPD-L1, sCD137, cytokine panel, RO, PD-L1 IHC, TMB, TCRseq, MSI and mRNA/IF may be adjusted for Part B, following availability of Part A data; conduct of RO assay (for Part A and B) will be dependent on availability of a suitable assay.

- a. Serial PK samples will be collected from all the patients enrolled in Part A and A-2. For the patients in Part B serial PK is optional except for the mandatory pre-dose, EOI and 168 ± 24 h sampling timepoints (see footnote "g").
- b. If a patient permanently discontinues study drug treatment, or is not receiving an infusion at a given visit, a single PK sample will be taken at that visit.
- c. Optional biopsy material for patients enrolled in Part A and A-2 from as many cycles as possible, and Follow-up period. For patients in Part B, a single post treatment biopsy material collection is considered mandatory per footnote "r" in [Table 7-1](#), i.e., for patients presenting with at least stable disease during treatment with NM21-1480.
- d. Optional sampling point for Part B. Sites are not required to collect these optional PK samples in Part B. These sampling timepoints are however mandatory in Part A and Part A-2. For sampling timepoints considered mandatory in Part B at all sites, see also footnote "g".
- e. EOI: End of Infusion. This sample should be taken immediately prior to stopping the infusion from the counter arm of the site of injection. All subsequent timepoints indicated for PK blood draws refer to hours *after* EOI.
- f. For FU visits: PK and ADA sample will be taken at Follow-up Visit 1 only.
- g. Mandatory sample for all patients in Part A, Part A-2 and Part B (unless drawing is not considered clinically feasible due to the condition of the patient).
- h. Only applicable for mCRC patients enrolled to Cohort B8. For specifics on sample acquisition please refer to specialty lab manual.
- i. Reference is made to footnote gg in Table 7-1 for timing of these mandatory on-treatment biopsies for mCRC patients enrolled to Cohort B8.
- j. Not applicable to patients in Cohort B5 randomized to standard-of-care anti-PD1 therapy only.
- k. Only applicable for mCRC patients enrolled to Cohort B8.

Table 7-4 Backup Pharmacokinetics, Anti-Drug Antibody, and Pharmacodynamic Blood Sampling Schedule (3-week Dosing Interval: APPLICABLE TO PART A-2 AND B ONLY IN CASE OF A POTENTIAL FUTURE SMC DECISION TO PROLONG DOSING INTERVAL#)

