3.5.2 Handling Missing or Below the Lower Limit of Quantification Data

For PK concentration data, if the actual sampling time is missing, but a valid concentration value has been measured, the concentration value will be flagged, and the scheduled nominal time point may be used for the calculation of PK parameters.

In cases of missing pre-dose concentrations prior to the first dose of Cycle 1, the missing concentration value may be imputed as zero. If missing pre-dose concentrations of Cycle 3, the pre-dose of Cycle 4 (or any cycle after Cycle 3) may be used as pre-dose concentration values. For the other cases, the missing data will not be imputed.

For the individual concentration and PK parameter calculation for Part A and A-2 by dose level and cycle and Part B by cohort and cycle, the following rules will be applied:

- If one or more below the limit of quantitation (BLQ) values occur before the first measurable concentration, they will be assigned a value of zero.
- If BLQ values occur between measurable concentrations in a profile, the BLQ should be omitted (set to missing).
- If BLQ values occur after the last measurable concentration in a profile, the BLQ should be omitted (set to missing).

For the concentration summary of NM21-1480 and mean (±SD) concentration plot preparation for Part A and A-2 by dose level and cycle and Part B by cohort and cycle, the following rules will be applied:

- Mean concentration at any individual time point will only be calculated if at least half of the patients have valid values (i.e. quantifiable and not missing) at this time point for each dose level, cohort and cycle.
- In cases where a mean value is not calculated due to the above criterion not being met, the value will be set to missing.
- BLQ values will be set to zero.
- The value of zero will be excluded from the calculation of GM and GM CV%

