Accumulation Index (AR _{AUC})	Accumulation ratios assessment of AUC; calculated as AUC _{tau} in Cycle 3 divided by AUC _{tau} in Cycle 1	Cycle 3

Actual collection times will be used in PK parameter calculations. The Linear-Log Trapezoidal method (equivalent to the Linear Up/Log Down option in WinNonlin) will be used in the computation of all AUC values. In order to estimate the apparent first-order terminal elimination constant, λ_z , linear regression of concentration in logarithm scale vs. time will be performed using at least 3 data points post C_{max}. Uniform weighting will be selected to perform the regression analysis to estimate λ_z . The constant λ_z will not be assigned if one of the following occurs:

1. The terminal elimination phase is not linear (as it appears on a semi-logarithmic scale).
2. The terminal elimination rate constant indicates a positive slope ($\lambda_z > 0$).
3. T_{max} is one of the three last data points.

The constant λ_z and its derived parameters will be flagged and included in the statistical analysis if one of the following occurs:

1. The adjusted regression coefficient (R²) is less than 0.8.
2. The AUC_{%extrap} exceeds 20%.

No value for λ_z , AUC_{0-inf}, AUC_{%extrap}, CL, CLss, Vz, Vzss or t_{1/2} will be reported for cases that do not exhibit an acceptable terminal log-linear phase in the concentration-time profile.

No PK parameters will be calculated for patients with 2 or fewer detectable concentrations in their PK profile.

PK parameters will be listed per patient and summarized by dose level and cycle (combined for Part A and A-2) and by cohort and cycle (Part B). The summaries of PK parameters will use following descriptive statistics: n, arithmetic mean, standard deviation, geometric mean, geometric standard deviation, 95% CI geometric mean, coefficient of variation (CV%), geometric CV% (calculated as: gCV% = $\sqrt{e^{s^2}-1} * 100$; where s is the standard deviation of the log-transformed values), minimum, maximum and median. Tmax will include median, minimum and maximum. No descriptive statistics will be determined when fewer than three individual PK parameters are available.

All available data will be presented in patient data listings which will be sorted by patient and visit date as applicable.

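### The closing Cycle 3 PK draw is timed at about the end of the next infusion rather than before it, with no SAP rule to exclude it, and a missing Cycle 3 trough may be borrowed from eight weeks later

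*Protocol*

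**What the plan says.** **Dosing and closing draw.** Protocol 7.1 states "Each treatment cycle comprises 2 doses of study drug administered on Days 1 and 15", and Table 7-1 lists the second Cycle 3 infusion visit as "C3: Day 71±3 / Week 11". In Table 7-3 the interval opens at "Cycle 3, Day 1 / Study Day 57 ± 3" with a pre-dose sample and closes at "Cycle 3, Day 15 / Study Day 71 ± 3" with a PK sample timed 336 h ± 48 h. The corresponding Cycle 1 row, "Cycle 1, Day 15 / Study Day 15 ± 2", and the Cycle 2 Day 15 row are both labelled pre-dose. SAP 3.5.1 repeats the 336 h ± 48 h label. Under Table 7-3 footnote e, timed draws are counted from end of infusion; Protocol 8.1 gives an infusion length of about 60 to 90 minutes. The 336 h draw carries footnote d: "Optional sampling point for Part B. Sites are not required to collect these optional PK samples in Part B". It is mandatory in Parts A and A-2.

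**Use of the sample.** SAP 3.5.4 uses actual collection times and the linear-up/log-down rule, sets CLss as dose over Cycle 3 AUCtau, and defines "Accumulation ratios assessment of AUC" as Cycle 3 AUCtau over Cycle 1 AUCtau. SAP 3.5.3 keeps out-of-window samples in the parameter calculations. Neither section excludes a sample taken after the next infusion has begun.

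**Missing opening sample.** SAP 3.5.2 says: "If missing pre-dose concentrations of Cycle 3, the pre-dose of Cycle 4 (or any cycle after Cycle 3) may be used". After Cycle 3, Table 7-3 and SAP 3.5.1 schedule PK on Day 8 of even cycles and pre-dose on Day 1 of odd cycles. No Cycle 4 pre-dose PK sample is scheduled.

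**The concern.** AUCtau is meant to cover one dosing interval. A closing sample taken during or after the next infusion carries a new dose, and the trapezoid from 168 h then rises where the true curve falls. Cycle 3 AUCtau goes up, and CLss and the AUC accumulation ratio move with it. Cycle 1 closes with a labelled pre-dose sample, so the error does not cancel in the ratio. It runs towards reporting accumulation, and drug accumulation is what Protocol 7.1 (Part A-2, 1400 mg) and 8.1 (Part B) name as the reason the dosing interval may be reconsidered.

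The substitution rule raises a smaller, separate matter. It names a sample that is not scheduled and otherwise reaches at least eight weeks ahead. Protocol 7.1 reports anti-drug antibodies with rapid elimination and loss of exposure in a relevant fraction of patients at 24 to 240 mg.

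**Working it through.** **1. The nominal time.** Day 71 − Day 57 = 14 days × 24 = 336 h, which reproduces the plan's figure counted from infusion start to infusion start. The clock, however, starts at end of infusion. With an infusion of 1.0 to 1.5 h, the nominal draw is at 337.0 to 337.5 h after the Cycle 3 Day 1 start. The next infusion starts at 336 h and ends at 337.0 to 337.5 h, so the nominal draw coincides with its end.

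**2. The window.** ± 48 h gives 289.0–385.0 h (1.0 h infusion) or 289.5–385.5 h (1.5 h). The share after 336 h is 49.0/96 = 51% or 49.5/96 = 52%. Visit windows allow dosing intervals from (71 − 3) − (57 + 3) = 8 days to (71 + 3) − (57 − 3) = 20 days. At 12 days (288 h) or less the whole window is post-infusion; at 17 days (408 h) or more none of it is.

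**3. Size by hand.** Assumptions: one compartment, unit doses, 14-day half-life (Protocol 5.1.2 predicts about two weeks; observed human values are not given), Cycle 3 Day 1 = fifth dose.
- Peak: 1 + 0.5 + 0.25 + 0.125 + 0.0625 = 1.9375
- At 168 h: 1.9375 × 2^(−0.5) = 1.3700
- Before the next dose: 0.96875; after it: 1.96875
- k = ln 2/336 = 0.002063 per h; true AUCtau = (1.9375 − 0.96875)/k = 469.6
- Segment 168–336 h, correct (log-down): 168 × (1.3700 − 0.96875)/0.34657 = 194.5
- Same segment with the post-dose value (linear-up): 168 × (1.3700 + 1.96875)/2 = 280.5
- Error: (280.5 − 194.5)/469.6 = +18%
- Accumulation ratio: 1.94 becomes about 2.29; CLss factor 1/1.18 = 0.85, i.e. −15%

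**4. Size in the fuller model.** 1.25 h infusion, all Table 7-3 Cycle 3 times, linear-up/log-down over 0–336 h:

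| Assumed half-life | AUCtau, draw at EOI + 336 h | CLss | Accumulation ratio, correct → read | AUCtau, draw at EOI + 384 h |
|---|---|---|---|---|
| 5 d | +50% | −33% | 1.17 → 1.75 | +32% |
| 7 d | +35% | −26% | 1.33 → 1.81 | +24% |
| 14 d | +18% | −15% | 1.94 → 2.29 | +13% |
| 21 d | +13% | −11% | 2.44 → 2.75 | +10% |

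**5. The opening sample.** The next Day 1 pre-dose is Day 113; 113 − 57 = 56 days. The opening value enters AUCtau only through the segment up to end of infusion, with weight 1.25/2 = 0.625 h. At 14 days, setting it to zero removes 0.625 × 0.9375 = 0.586, or 0.586/469.6 = 0.12%. Over 5 to 21 days the loss is 0.06% to 0.14%. Using the Cycle 5 value instead adds at most 0.02%. Cmin is different. At 14 days with exposure maintained it reads 0.96875/0.9375 = 1.03 times the true value; if exposure is gone by Cycle 5, it becomes zero, and the Cmin accumulation ratio with it.

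**The case against.** The strongest reply is that sites will draw before the infusion anyway, as they do on Day 15 of Cycles 1 and 2. That may be so: the documents do not show how many draws, if any, were late, and a correctly timed draw gives no bias. But the written time points to the end of the infusion, so correct practice would depend on sites departing from the nominal label.

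A second reply is that SAP 3.5.4 already guards against this. It withholds λz when the terminal phase is not log-linear, the slope is positive, or Tmax is among the last three points, and withholds CLss and the terminal volumes when that phase is unacceptable. This is partial protection. AUCtau and the AUC accumulation ratio are not on the withheld list, and CLss survives if the slope is fitted to earlier points.

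Third, neither Protocol 7.1 nor 8.1 makes the AUC ratio a decision criterion, and the pre-dose samples up to Cycle 3 Day 1 do not depend on this draw. That stands. A reader might infer that past interval decisions were distorted. The documents do not support this: Part A reported no substantial accumulation, and this error would push the other way.

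A reader might also infer that Part B needs a mandatory 336 h tube, or the three-week schedule a further row. Sparse Part B sampling is a stated choice: Table 7-3 footnote a makes serial PK optional, Protocol 9.3 derives parameters for patients with serial samples, and 10.6.10 directs limited sampling to population PK. Table 7-4 is a contingent backup that requires an amendment before use.

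**Conclusion.** The point holds as a mislabelled sample with no exclusion rule behind it. If the Cycle 3 Day 15 draw is taken after the infusion starts, AUCtau and the AUC accumulation ratio are overstated and CLss, where still reported, is understated: about +18%, 2.29 for 1.94, and −15% at a 14-day half-life. The sizes rest on an assumed half-life, one compartment, full serial sampling and a draw at nominal time. The direction follows from adding a dose to the closing value.

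The substitution rule is a lesser defect, confined to Cmin, its accumulation ratio and troughs in patients who lose exposure. Two stronger readings fail. A borrowed opening sample does not materially bias AUCtau or CLss (less than 0.15%). Nor is the rule impossible to carry out: it is permissive and extends to any later cycle, so the Cycle 5 pre-dose can be used. Protocol 7.1 reports no such loss of exposure at 800 mg, so the risk lies mainly with the lower Part A doses.

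**What to change.** 1. **Table 7-3 and SAP 3.5.1:** label the Cycle 3 Day 15 PK draw pre-dose, as in Cycles 1 and 2.
2. **SAP 3.5.4:** exclude any sample taken after the start of the next infusion from the Cycle 3 profile, covering AUCtau, Cmin, λz and the parameters derived from them.
3. **SAP 3.5.2:** delete the later-cycle substitution and leave a missing Cycle 3 pre-dose unimputed.

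These are wording changes. The exclusion will cost some patients an observed end to the interval, which is preferable to a value from the next dose. Not imputing the opening value costs AUCtau almost nothing: the whole segment to end of infusion is (0.9375 + 1.9375)/2 × 1.25 = 1.80, or 0.4% of 469.6. SAP sections 4 and 6 record early closure and limited enrolment, so the table relabelling now mainly corrects the record. The changes to 3.5.2 and 3.5.4 can still affect results and belong in the SAP before database lock, when section 1 says it is to be final.
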